1 INTRODUCTION

The purpose of this Statistical Analysis Plan (SAP) is to provide details of the statistical analyses that have been outlined within the UX023-CL205 Protocol Amendment 1 dated 28 March 2016. The SAP for Week 4 analysis was pre-specified in a separate document (UX023-CL205 Statistical Analysis Plan Week 4 Analysis) before the analysis took place.

2 STUDY OBJECTIVE(S)

2.1 Primary Objective

The primary objectives of the study are to:

- Establish the safety profile of KRN23 for the treatment of XLH in children between 1 and 4 years old
- Determine the PD effects of KRN23 treatment on serum phosphorus and other PD markers that reflect the status of phosphate homeostasis in children between 1 and 4 years old with XLH

2.2 Other Objective

Additional study objectives are to assess the following in children between 1 and 4 years old with XLH:

- Effects of KRN23 on rickets
- Effects of KRN23 on growth and lower extremity deformity
- Pre-dose KRN23 drug concentration levels

3 STUDY DESIGN

As background for the statistical methods presented below, this section provides an overview of the study design. This overview is a summary only. The protocol is the definitive reference for all matters discussed in what follows.

3.1 Study Population

UX023-CL205 is a multicenter, open-label, Phase 2 study in children from 1 to 4 years old with XLH who are naïve to therapy or have previously received standard therapy with oral phosphate and active vitamin D to assess the safety, PD, and efficacy of KRN23 administered via subcutaneous injections Q2W for a total of 64 weeks.

3.2 Dosage and Administration

The length of this study will be 64 weeks. All subjects will receive KRN23 at a starting dose of 0.8 mg/kg every two weeks (Q2W). The dose may be increased to 1.2 mg/kg at any time if a subject meets the following dose adjustment criteria: 1) two consecutive serum phosphorus measurements are below the normal range; 2) serum phosphorus has increased by < 0.5 mg/dL from baseline; and 3) the subject has not missed a dose of study drug that would account for the decrease in serum phosphorus.

At any time during the study, if serum phosphorus increases above the upper limit of normal for age, the subsequent dose(s) will be withheld and the site will contact the medical monitor before dosing resumes. Once other causes of increased serum phosphorus are excluded, KRN23 treatment will resume at half the total dose of the last dose received. Serum phosphorus will be followed through unscheduled serum phosphorus assessments. A subject will resume dosing at the previous full total dose level if they meet the same dose-adjustment criteria listed above.

Serum phosphorus assessments will be conducted at the clinic at the ends of Weeks 1, 4, 8, 12, 15, 20, 32, 40, 48, 56 and 64. Growth (recumbent length/standing height) assessment will be conducted at the ends of Week 12, 24, 40 and 64. Bilateral AP knee X-rays, bilateral PA hand/wrist X-rays and standing long leg X-rays will be conducted at Week 40 and 64. The schedule of assessments is shown in [Appendix 3](#).

3.3 Blinding and Randomization Methods

The UX023-CL205 is an open-label Phase 2 study; all subjects will receive same starting dose Q2W. Blinding or randomization methods are not applicable for this study.

3.4 Stratification Factors

Stratification factors are not applicable for this study.

3.5 Sample Size Considerations

The study will enroll approximately 10 pediatric subjects between 1 and 4 years old, inclusive, with clinical findings consistent with XLH including hypophosphatemia and radiographic evidence of rickets (at least 5 subjects will have a rickets severity score (RSS) at the knee of ≥ 1.5 points at Screening), and a confirmed *PHEX* mutation or variant of uncertain significance. To maintain a level of gender balance, no more than 7 subjects of either gender will be enrolled.

3.6 Planned Analyses

The primary analysis is planned at Week 40. Additional efficacy and safety analyses will be conducted at Week 64. A Week 24 analysis has been planned as an administrative analysis to support regulatory interaction. The analysis will include safety, Pharmacokinetics (PK), Pharmacodynamics (PD), and growth assessments; rickets assessment from radiographs will not be included as the radiographs are not scheduled until Week 40. Additional administrative analyses may be done at the sponsor's discretion to support regulatory submission or product planning.

3.7 Data Monitoring Committee

An independent DMC that includes members with expertise in metabolic bone disease, cardiology, nephrology, and the conduct of clinical trials in children will act in an advisory capacity to monitor subject safety on a routine basis throughout the trial. The DMC will meet approximately twice a year. The roles and responsibilities of the DMC will be defined in the DMC Charter.

4 STUDY ENDPOINTS, COVARIATES

All data are collected according to the schedule of assessments ([Appendix 3](#)).

4.1 Primary Efficacy Endpoints

The primary efficacy endpoint is the change from baseline in serum phosphorus.

4.2 Secondary Efficacy Endpoints

The secondary efficacy endpoints include

- Change in rickets at Week 40 as assessed by the Radiograph Global Impression of Change (RGI-C) global score
- Change in rickets at Week 64 as assessed by RGI-C global score
- Change from baseline in Rickets Severity Score (RSS) total score at Weeks 40 and 64
- Change in lower extremity skeletal abnormalities, including genu varum and genu valgus, as determined by the RGI-C long leg score at Weeks 40 and 64
- Change in recumbent length/standing height from baseline to post-treatment study time points in cm, height-for-age z-scores, and percentiles. Historical growth records may be used to evaluate change in growth velocity
- Change and percent change from baseline over time in serum alkaline phosphatase (ALP)

4.3 Other Efficacy Endpoints

Other efficacy endpoints include

- Change from baseline over time in serum 1,25(OH)₂D and urinary phosphorus
- Change in rickets at Week 40 and 64 as assessed by RGI-C wrist score and knee score
- Change from baseline in RSS wrist score and knee scores at Week 40 and 64

4.4 Safety Endpoints

General Safety Variables will include the following:

- Treatment Emergent Adverse Events (TEAEs)
- Treatment Related TEAEs
- Treatment Emergent Serious Adverse Events (TESAEs)
- Events to monitor:
 - Injection site reaction (High-Level Term)
 - Immunogenicity

- Hyperphosphatemia
- Ectopic mineralization
- Restless leg syndrome
- Grade 3/4 TEAEs
- TEAEs leading to discontinuation from the study
- TEAEs leading to discontinuation from the study drug treatment
- TEAEs leading to death
- Vital signs and weight
- Physical examinations
- Estimated Glomerular Filtration Rate (eGFR)
- Chemistry, hematology, and urinalysis, including additional KRN23/XLH biochemical parameters of interest (serum calcium, intact parathyroid hormone[iPTH], 25-hydroxyvitamin D [25(OH)D], amylase, lipase, and creatinine; and urinary calcium and creatinine)
- FGF23
- Anti-KRN23 antibody (HAHA) testing and Dose-Limiting Toxicities (DLT)
- Concomitant medications

Ectopic Mineralization Safety Assessments include:

- Renal ultrasound
- Electrocardiogram (ECG)

4.5 Drug Concentration Measure

To assess KRN23 concentration and possible accumulation, serum pre-dose levels will be evaluated as a PK parameter in this study.

4.6 Covariate(s)

Baseline measures will be used as covariates. For example, baseline RSS score will be used in the modeling for change in baseline in RSS score and for RGI-C score. Age and gender may also be used as covariates in growth endpoint models.

5 DEFINITIONS

5.1 Baseline

Baseline is defined as the last assessments prior to or on the date of initiation of the first dose of investigational product.

5.2 Study Day

Study day is calculated as:

(visit date – date of the first dose of investigational product + 1) if the visit data is on or after the first dose of investigational product; or (visit date – date of the first dose of investigational product) if the visit data is prior the first dose of investigational product.

5.3 Age

Unless specified, the age will be derived based on the informed consent date: Age = (Informed Consent Date – Birth Date +1)/365.25. The age will be rounded down to the nearest x.x years and keep one decimal place.

5.4 RGI-C

Changes in the severity of rickets and bowing will be assessed centrally by three independent pediatric radiologists contracted by a central imaging facility using a disease specific qualitative Radiographic Global Impression of Change (RGI-C) scoring system.

The RGI-C is a seven point ordinal scale with possible values:

- +3 = very much better (complete or near complete healing of rickets),
- +2 = much better (substantial healing of rickets),
- +1 = minimally better (i.e., minimal healing of rickets),
- 0 = unchanged,
- 1 = minimally worse (minimal worsening of rickets),
- 2 = much worse (moderate worsening of rickets),
- 3 = very much worse (severe worsening of rickets),

Raters will be presented with side-by-side images taken from subjects during the UX023-CL205 study with the Baseline image on the left (Image A) and Post-Treatment image (Week 40 and Week 64) on the right (Image B). Raters will be asked to evaluate change in Image B for the abnormalities they consider to be present in the Baseline Image A. This exercise will be performed for the distal radius and ulna from the bilateral wrist X-rays, and the distal femur and proximal tibia and fibula from the bilateral knee X-rays at Week 40 and Week 64. At Week 64, Image A (presented on the left) will remain the Baseline image and Image B (presented on the right) will be the post-treatment image from Week 64.

In addition to bilateral wrists and knees, the Week 40 and Week 64 RGI-C analysis will include a rating of the full femur, tibia and fibula from the bilateral standing long leg film with the Baseline standing long leg image on the left (Image A) and the Week 40 (or Week 64) standing long leg image on the right (Image B). The RGI-C is scored using a pre-defined methodology ([Biomedical Systems Independent Review Manual July 2015](#)). See data collection form in [Appendix 5](#).

Prior to rating, the three raters will be trained to gain consensus on the terminology used to describe XLH-related radiographic abnormalities and to establish inter-rater reliability. Following the training, each rater will independently complete a quiz involving the rating of practice images to ensure the success of the training and the reliability of scores among the raters. For the Week 40 and Week 64 analysis, each of the three raters will perform the rating exercise at a work station at the central imaging facility. Only one rater can be present at the facility at any given time to prevent group rating or sharing of scores. Each rater will be presented with side-by-side images of the wrist and knee with Baseline on the left (Image A) and Post-Treatment on the right (Image B). Raters will be asked to evaluate the presence of various abnormalities in the wrist and knee in Image A and change in those abnormalities in Image B. At the Week 40 and Week 64 analysis, each rater will evaluate changes in rickets severity from Baseline to Week 40 in the wrists and knees by assigning a regional score for the wrist, a regional score for the knee, as well as an overall impression score (RGI-C global score). The RGI-C scores for the three raters will be averaged and the mean scores for the wrist, knee and overall impression will be reported. The raters will also evaluate images from long leg radiographs. The RGI-C scores from the three raters will be averaged to generate a RGI-C lower limb deformity score. RGI-C scores will be entered into an EDC system at the time of the scoring and cannot be retrieved or changed by the rater after submission. RGI-C scores will be transferred electronically from the imaging facility to Ultragenyx after the image rating exercise is complete.

RGI-C response is defined as an averaged RGI-C global score of at least +2.0 (i.e. substantial healing of rickets).

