8.8.3 Secondary Efficacy Endpoints

8.8.3.1 RGI-C

The efficacy analyses evaluating RGI-C scores will be performed at Week 40 and Week 64. The GEE model will be applied to each RGI-C score type (wrist, knee, global and lower limb deformity) separately to obtain 95% CIs and p-values. Baseline RSS score will be included as a covariate in the model; age may also be included as covariate in the model.

As sensitivity analysis, t test will be performed for RGI-C scores at Week 40 and Week 64. In the case when model assumption is not met, analyses using alternative methods such as non-parametric tests will be performed.

Descriptive statistics for all RGI-C scores will be provided in both continuous and categorical summary. RGI-C responder rate will be calculated. Summary of abnormality at baseline and change in abnormality at Week 40 and Week 64 will also be presented.

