Appendix 5: RGI-C Data Collection Form

REGIONAL RATING OF RICKETS

How would you rate the change in XLH-related rickets in the HANDS/WRISTS? *Circle one*

-3	-2	-1	0	+1	+2	+3
Severe Worsening	Moderate Worsening	Minimal Worsening	No Change	Minimal Healing	Substantial Healing	Complete or Near Complete Healing

Identify abnormalities in image **A** on the left and then rate any change seen in image **B** on the right compared to image **A**

PA HAND/WRIST SINGLE ABNORMALITY RATING

BILATERAL PA RADIUS		NOT in "A"	DECREASED	UNCHANGED	INCREASED
	Metaphyseal lucency				
	Metaphyseal/epiphyseal separation				
	Metaphyseal fraying				
	Metaphyseal concavity				
BILATERAL PA Ulna		NOT in "A"	DECREASED	UNCHANGED	INCREASED
	Metaphyseal lucency				
	Metaphyseal/epiphyseal separation				
	Metaphyseal fraying				
	Metaphyseal concavity				

REGIONAL RATING OF RICKETS

How would you rate the change in XLH-related rickets in the KNEES? *Circle one*

-3	-2	-1	0	+1	+2	+3
Severe Worsening	Moderate Worsening	Minimal Worsening	No Change	Minimal Healing	Substantial Healing	Complete or Near Complete Healing

Identify abnormalities in image **A** on the left and then rate any change seen in image **B** on the right compared to image **A**

AP KNEES SINGLE ABNORMALITY RATING

BILATERAL AP FEMUR	NOT in "A"	DECREASED	UNCHANGED	INCREASED
Metaphyseal lucency				
Metaphyseal/epiphyseal separation				
Metaphyseal fraying				

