Metaphyseal concavity				

AP KNEES SINGLE ABNORMALITY RATING

BILATERAL AP TIBIA	NOT in "A"	DECREASED	UNCHANGED	INCREASED
Metaphyseal lucency				
Metaphyseal/epiphyseal separation				
Metaphyseal fraying				
Metaphyseal concavity				

BILATERAL AP FIBULA	NOT in "A"	DECREASED	UNCHANGED	INCREASED
Metaphyseal lucency				
Metaphyseal/epiphyseal separation				
Metaphyseal fraying				
Metaphyseal concavity				

GLOBAL RATING OF RICKETS

How would you rate the change in XLH-related rickets?

The **B** images on the right as compared to **A** images on the left show *circle one*

-3	-2	-1	0	+1	+2	+3
Severe Worsening	Moderate Worsening	Minimal Worsening	No Change	Minimal Healing	Substantial Healing	Complete or Near Complete Healing

RATING OF LOWER LIMB DEFORMITY

How would you rate the change in XLH-related lower limb deformity? *Circle one*

-3	-2	-1	0	+1	+2	+3
Severe Worsening	Moderate Worsening	Minimal Worsening	No Change	Minimal Healing	Substantial Healing	Complete or Near Complete Healing

[figure not shown]
Identify abnormalities in image **A** on the left and then rate any change seen in image **B** on the right compared to image **A**

SINGLE ABNORMALITY RATING

[figure not shown]
STANDING LONG LEG	NOT in "A"	VARUS	VALGUS	DECREASED	UNCHANGED	INCREASED
L Tibia						
R Tibia						
L Fibula						
R Fibula						
L Femur						
R Femur						

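### Does the RGI-C abnormality checklist need a separate code for a lesion absent at baseline and present on treatment?

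*SAP*

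**What the plan says.** Section 5.4 of the SAP describes the lesion read twice. The first description is "Raters will be asked to evaluate change in Image B for the abnormalities they consider to be present in the Baseline Image A". The second, for the reading sessions, has raters "evaluate the presence of various abnormalities in the wrist and knee in Image A and change in those abnormalities in Image B". Both start from what is visible in the baseline film.

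The scores are described separately in the same section: "each rater will evaluate changes in rickets severity from Baseline to Week 40 in the wrists and knees by assigning a regional score". There is one such score per region, together with a global score. Section 5.4 also says "The RGI-C is scored using a pre-defined methodology" and cites an independent review manual. It adds that the raters are trained on terminology and must complete a quiz before reading.

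Appendix 5 carries the form. The blocks headed "PA HAND/WRIST SINGLE ABNORMALITY RATING" and "AP KNEES SINGLE ABNORMALITY RATING" have one row per feature and bone, each with four boxes: not in A, decreased, unchanged, increased. The instruction above the rows has the rater identify abnormalities in image A "on the left and then rate any change seen in image" B.

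The analysis of these boxes is one sentence in section 8.8.3.1: "Summary of abnormality at baseline and change in abnormality at Week 40 and Week 64 will also be presented".

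**The concern.** A checklist anchored to the baseline film can show existing lesions healing, standing still or worsening. It has no labelled place for a lesion that first appears on treatment. Read literally, such a lesion falls under not in A, together with lesions that never appear at all. In a single-arm trial, a lesion-level table that can miss one direction of change would tend to flatter the treatment.

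The entry rule adds to the worry. Section 3.5 requires only about half of the roughly 10 children to have a knee RSS of 1.5 or more. The others may have few knee lesions at baseline, which leaves more rows where a new lesion could arise. If a child's other lesions were healing, a new one might also be outweighed in a net impression score.

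**Working it through.** No plan figure is involved, so the check sets the possible states of a lesion against the boxes and then follows the boxes into the analysis.

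**Rows (Appendix 5).** Wrist: 2 bones (radius, ulna) x 4 features = 8. Knee: 3 bones (femur, tibia, fibula) x 4 features = 12. Total 8 + 12 = 20. The long-leg table is broken in the text and is not counted.

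**States against boxes.** One feature in one bone has five possible states; the form has four boxes.

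| Image A | Image B | Box |
|---|---|---|
| absent | absent | not in A |
| absent | present | none labelled |
| present | less | decreased |
| present | same | unchanged |
| present | more | increased |

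The second line is the gap, and it applies to all 20 rows.

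**How a rater could mark a new lesion.** The form asks for any change seen and states no one-tick rule. That leaves three possibilities:

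1. Not in A alone: the new lesion is merged with lesions never present.
2. Increased alone: it is counted as worsening, but merged with worsening of an existing lesion.
3. Not in A plus increased: the pair identifies a new lesion exactly.

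The SAP does not choose between them. The cited manual may.

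**Can the loss be sized?** With about 10 children there are 20 x 10 = 200 child-rows per rater per visit. If 25%, 50% or 75% were absent at baseline (assumed), that is 200 x 0.25 = 50, 200 x 0.50 = 100 or 200 x 0.75 = 150 rows. If 1, 2 or 3 of 10 children developed a new lesion (assumed) and no existing lesion worsened, the table would show 0% of children worsening instead of 10%, 20% or 30%. Both sets of figures hold only under possibility 1 for every rater; under 2 or 3 the worsening is recorded. The row counts also overstate the loss even then, because information goes missing only where a new lesion actually appears, not in every row that starts empty. The documents do not say how often that happens.

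**Baseline severity.** In Appendix 4 each knee bone scores a grade of 1 to 3 times 0.5 or 1, so knee totals move in steps of 0.5 and a total below 1.5 is at most 1.0 of 6. Up to about 10 - 5 = 5 children could enter there. Section 3.5 nevertheless describes all subjects as having radiographic evidence of rickets, and a low knee score says nothing about the 8 wrist rows.

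**Where the boxes go.** Sections 4.1 to 4.3 and Appendix 1 list RGI-C scores and RSS scores, not the checklist. Section 5.4 defines response from the averaged global score. No score is computed from the boxes.

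**The case for a change.** The strongest case for a change is that nothing else in the plan reports lesion by lesion. The RGI-C scores are net impressions. The RSS grades only the more severe side (section 5.5), has no fibula item (Appendix 4) although 4 of the 20 checklist rows are fibula, and is analysed only as wrist, knee and total. Submitted scores cannot be altered by the rater, so a convention missing at the Week 40 read could be recovered only by reading again. The manual was written for another study, and an extra box per row is cheap.

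Part of this stands. On the SAP's text a new lesion is not separately identifiable, and three raters without a shared convention could tick differently.

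The rest is weaker. The RGI-C knee read in section 5.4 covers the fibula and both sides, so a new lesion there is in front of the rater who assigns the regional score. The RSS reader scores each film individually and blinded to visit, so that read is not anchored to baseline at all. An extra box would also depart from a form whose manual comes from an earlier study, at some cost to like-for-like reading, in exchange for one descriptive line. If the manual already fixes the convention, nothing is missing.

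**Conclusion.** The observation is correct: none of the 20 wrist and knee rows has a defined code for a new lesion. No change to the plan follows. Rating change in lesions seen at baseline is a fair design for a change-from-baseline instrument, and overall worsening has its own routes through the scores and the RSS. The primary endpoint, the RGI-C scores, the responder rate and the RSS results are the same whichever way a new lesion is ticked.

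The effect is confined to one descriptive table, and its size cannot be given from the documents. The 10% to 30% illustration rests on assumed numbers of new lesions and on every rater ticking not in A alone.

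What remains is a gap that the imaging group and the analyst can fill in ordinary work: the tick convention belongs with the manual and the rater training, and the table can be read as change in abnormalities present at baseline. This conclusion assumes that the checklist keeps its descriptive role and is not offered as evidence that no new lesions occurred.

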5.5 RSS

The severity of rickets will be measured using a scale developed by [name] for the assessment of nutritional rickets ([Thacher et al. 2000](#)). This scale will be referred to as the RSS. The RSS system is a 10-point radiographic scoring method that was developed to assess the severity of nutritional rickets in the wrists and knees based on the degree of metaphyseal fraying, cupping, and the proportion of the growth plate affected. Scores are assigned for the unilateral wrist and knee X-rays deemed by the rater to be the more severe of the bilateral images. The maximum total score on the RSS is 10 points, with a total possible score of 4 points for the wrists and 6 points for the knees. Higher scores indicate greater rickets severity. The RSS is scored using a pre-defined methodology ([Biomedical Systems Independent Review Manual September 2014](#)). Each radiograph is scored individually by [name] who will serve as the single central independent rater for all UX023-CL205 X-rays taken at Baseline, Week 40 and Week 64. For the X-rays taken during the

UX023-CL205 study, [name] will be blinded to the study visit at which the X-ray was taken, adherence to the study protocol and duration of treatment. Each rating performed by [name] is entered into an EDC system at the time of the rating and transferred electronically to a central imaging facility. The scores cannot be retrieved from the system by [name] after submission. See RSS data collection form in [Appendix 4](#).

